Eligible women can enroll between 20 0/7 -37 6/7 weeks gestation or 2-12 weeks postpartum, depending on study arm. All infants of mothers enrolled during pregnancy will be enrolled in utero, after maternal enrollment. Enrolled infants who meet the requirements for washout PK sampling will undergo PK sampling. HIV-infected pregnant women without TB will be followed for 6 – 12 weeks after delivery with the exception of women on DRV/r who will be followed for 2 – 3 weeks after delivery. HIV-infected and non-infected women receiving TB treatment (first or second line) will be followed for 2 – 8 weeks after delivery. Postpartum women will be followed until 6 – 7 weeks after the initiation of hormonal contraceptives. Infants will be followed for 16 – 24 weeks of life.

Analyses for the Final Analysis Report for each study arm will be done once the last participant in that arm has completed all study visits, laboratory assays have been completed, and all queries have been resolved.

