
*Stage 1 analysis for the TB drugs will not be done in real time and will only be done when batched PK data are available (unlike the Stage I analysis for ARVs).  **This comparison may have a smaller sample size than 25 because some women may complete their TB treatment before the postpartum PK visit.  #Interim AUC monitoring (Stage 1 analysis) is not done for these arms (only done during pregnancy).
			

In Stage 1, an individual woman’s PK exposure parameter during pregnancy will be compared in real time to the 10th percentile for that PK exposure parameter for that drug from a non-pregnant population, and the woman and her clinical provider will be notified if the woman’s value is below the 10th percentile. If there is strong evidence that the true percentage of pregnant women having the PK exposure parameter below the 10th percentile for the non-pregnant population is greater than 10%, the study team will evaluate whether to stop enrollment early and whether to recommend that additional study of the drug/drug combination is necessary.

Stage 2 for the ARV drugs taken during pregnancy will implement a repeated measures design, in which antepartum and postpartum measurements from each woman will be compared. This stage requires a minimum of 12 participants in each arm to have postpartum PK measurements. If less than 12 participants out of the 25 in any arm have postpartum measurements, more participants will be enrolled in that arm until the minimum postpartum measurement number of 12

is reached. The comparisons will be made at the within-participant level, using the Wilcoxon signed rank test to assess whether there is a statistically significant difference in the PK exposure parameter in the pregnant versus non-pregnant conditions. 90% confidence limits for the geometric mean ratio of the PK exposure parameter in the pregnant versus non-pregnant conditions will also be calculated to describe the range of values that are consistent with the observed data and help the Protocol Team assess whether there is a clinically important difference in exposure in the pregnant versus non-pregnant conditions.

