For the second line TB drugs, the PK analysis will use the Stage 2 approach described above, in which a within-participants comparison of TB drug PK exposure during pregnancy and postpartum will be performed. Note that the sample size for these comparisons may be less than the desired 25 evaluable women per drug because the inclusion criteria for this study arm only require that women are receiving at least two of the specified second line TB drugs, and because some women may complete their TB medication course before the postpartum visit where the PK sampling will be done. It may or may not be possible to perform a Stage 3 between-participants comparison of second line TB drug PK exposure in HIV-infected versus HIV-uninfected women; depending on the number of women receiving each TB drug, it may be necessary to combine data from HIV-infected and HIV-uninfected women.

For the ARV drugs being taken with postpartum contraceptives, the Stage 1 analysis above will not be performed (the Stage 1 analysis will only be done for ARV during pregnancy). A within-participants analysis similar to the Stage 2 analysis described above will be performed, except

that the ARV PK exposure parameters before versus after starting contraceptives will be compared (instead of during pregnancy versus postpartum).

For the contraceptives, a Stage 3 analysis will be performed that will compare the contraceptive concentrations observed in P1026s women receiving a protease inhibitor to data from historical controls not receiving ARVs, as reported in the available literature.

For analyses of PK secondary objectives, descriptive statistics (mean, median, standard deviation, interquartile range, and range) will be tabulated for PK outcome measures. If most infant washout PK data are below the BLQ for a given study arm, the pharmacologist may determine that the analysis report should not include an infant washout PK data summary (this will be noted in the report).

For the secondary objectives related to safety and clinical outcomes, adverse events and other safety outcome measures will be tabulated, and descriptive statistics (mean, median, standard deviation, interquartile range, and range) will be calculated for CD4 and HIV-1 RNA measurements (for HIV-infected participants only).

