#### **4.1 Statistical Tests**

Within-participant comparisons (e.g., between pregnant versus non-pregnant conditions or second versus third trimester) will be performed for continuous outcome measures using the Wilcoxon signed rank test and for dichotomous outcome measures using McNemar's test. If the statisticians determine there are not enough women with PK data available at both time points for a meaningful comparison, then no p-value will be calculated. In addition, if there are no discordant pairs for McNemar's test, then the test will not be performed. Between-participant comparisons will be performed for continuous outcome measures using the Wilcoxon rank sum test and for dichotomous outcome measures using the chi-square or Fisher exact test.

90% confidence limits for the geometric mean ratio of the PK exposure parameter in the pregnant versus non-pregnant conditions will also be calculated to describe the range of values that are consistent with the observed data and help the Protocol Team assess whether there is a clinically important difference in exposure in the two conditions. The confidence coefficient will be 90% rather than 95% to match the usual practice in the pharmacokinetic literature to show that two conditions are sufficiently similar (e.g, bioequivalence testing).

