#### **4.2 Limitation**

The P1026s study design is opportunistic in that it enrolls women who are already receiving the study drugs as part of clinical care, but this design has one major limitation, namely that the results may be overly optimistic. Since participants must have been stable on the ARV drug/drug combination and/or TB drug combination for at least two weeks prior to PK sampling in order to enroll in the study, the study population will not include women who started the study drug and discontinued it within two weeks due to toxicity, intolerance, virologic failure, or any other reason. Thus, this study will not be able to identify pharmacokinetic, safety, or tolerance issues that occur very soon after drug initiation and estimates of the frequency of outcomes such as virologic response and mother-to-child HIV transmission may be overly optimistic. The fact that the results

of this study will generalize only to the population of women who are able to stay on the study drugs for at least two weeks will be discussed as a limitation of the study in presentations and publications of results. The Protocol Team acknowledges this limitation, but feels that the PK data obtained using the current design will still be quite valuable nonetheless.

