## 5 Report Contents

Detailed descriptions of the content of each of the following sections are given in the AIP.

- 1) Maternal demographics summary
  - Race, ethnicity, and country
  - Age, gestational age, weeks after delivery and weight at PK visits
  - ARV/TB medication duration before antepartum visits; concomitant ARV/TB medications at antepartum visits
  - Viral load and CD4 at antepartum, delivery and postpartum visits
- 2) Maternal safety
  - List of AEs reported to Division of AIDS (DAIDS) as Expedited Adverse Events (EAEs)
  - List of Grade 3 or greater AEs
  - List of AEs that are possibly/probably/definitely related to study drugs, as determined by the Core Protocol Team and/or site investigators.
- 3) Maternal PK analysis (as applicable to study arm being analyzed)
  - PK descriptive summaries by parameter and study visit
  - PK parameter comparisons of antepartum vs. postpartum
  - Summary of mothers with AUC above 10th percentile in antepartum vs. postpartum
  - Summary of cord blood/maternal plasma ratio
- 4) Infant demographics
  - Birth weight, length, gestational age and most definitive HIV status
- 5) Infant safety
  - List of congenital anomalies
  - List of AEs reported to DAIDS as EAEs
  - List of Grade 3 or greater AEs
  - List of AEs that are possibly/probably/definitely related to study drugs, as determined by the Core Protocol Team and/or site investigators.
- 6) Infant PK analysis
  - Washout concentration and half-life summary

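### Stage 2 for second line TB drugs takes no account of time on drug, so for a slowly accumulating drug incomplete accumulation can look like lower exposure in pregnancy

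*SAP*

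**What the plan says.** Section 4 of the SAP plans for second line TB drugs that "a within-participants comparison of TB drug PK exposure during pregnancy and postpartum will be performed". Table 1 lists Stage 2 as the only comparison for these drugs. The text adds that a comparison by HIV status may or may not be feasible, but that comparison would not bear on this point.

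Stage 2 uses a Wilcoxon signed rank test, without covariates, for a "statistically significant difference in the PK exposure parameter in the pregnant versus non-pregnant conditions". Section 4.1 adds that "90% confidence limits for the geometric mean ratio of the PK exposure parameter in the pregnant versus non-pregnant conditions will also be calculated".

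The minimum time on drug appears in Section 4.2: "Since participants must have been stable on the ARV drug/drug combination and/or TB drug combination for at least two weeks prior to PK sampling". That section discusses the selection of women who tolerate the first two weeks. It does not mention accumulation.

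Section 3 makes evaluability depend on whether there are adequate PK evaluations, judged by a protocol pharmacologist. It states no steady-state or time-on-drug condition. Section 5 lists "ARV/TB medication duration before antepartum visits" among the maternal demographic summaries, and no comparison refers to it.

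**The concern.** Within each pair, pregnancy status and time on drug change together: the pregnant measurement is always the earlier one. If a drug has not reached steady state at the antepartum visit, the later postpartum measurement is higher for that reason alone. Without a loading regimen this pushes the antepartum/postpartum ratio down. Section 2.5 names lower exposure in pregnancy as the main worry for the ARV drugs, and a spurious fall would point the same way. The same bias could hide a true rise in exposure.

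More women do not help. A larger sample makes a biased ratio look more precise. Table 1 plans no Stage 1 comparison with a non-pregnant population for second line drugs, so no other listed result would expose the problem. Section 4 already warns that the first line Stage 3 comparison cannot separate ARV use from HIV infection, but Stage 2 carries no such caution about time on drug.

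**Working it through.** **Figure in the plan.** The SAP gives no half-life, variance, margin or power for Stage 2. Its one reproducible figure, the exact 80% limits for 6 of 25 women in Section 2.5, comes out at 0.131 to 0.383 and agrees with the stated (0.13, 0.38). It is not an input here.

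**Inputs from the SAP**
- Minimum time on drug: 14 days (Section 4.2).
- Antepartum window: "Eligible women can enroll between 20 0/7 -37 6/7 weeks gestation" (Section 2.1).
- Postpartum window: "women receiving TB treatment (first or second line) will be followed for 2 – 8 weeks after delivery" (Section 2.1).
- Pairs: target 25, possibly fewer per drug (Section 4).

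**Assumptions**
- Delivery at 40 weeks, with the postpartum sample 2 to 8 weeks later. The longest gap is (40 − 20) + 8 = 28 weeks. The shortest is about 2 + 2 = 4 weeks.
- First-order accumulation, constant dosing, no loading.
- Effective half-life T from 3 to 40 days. This range is illustrative.

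**Formula.** The fraction of steady state after d days is f(d) = 1 − 2^(−d/T). With no true pregnancy effect, the apparent ratio is f(d) / f(d + gap).

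Example with T = 20 days, sample at day 14, gap 84 days: f(14) = 1 − 2^(−0.7) = 0.384; f(98) = 1 − 2^(−4.9) = 0.967; ratio = 0.40.

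| Half-life | f(14) | Ratio at day 14; gap 4 / 12 / 28 weeks | Ratio at 8 weeks on drug; gap 4 / 12 / 28 weeks |
|---|---|---|---|
| 3 d | 0.96 | 0.96 / 0.96 / 0.96 | 1.00 / 1.00 / 1.00 |
| 5 d | 0.86 | 0.86 / 0.86 / 0.86 | 1.00 / 1.00 / 1.00 |
| 10 d | 0.62 | 0.66 / 0.62 / 0.62 | 0.98 / 0.98 / 0.98 |
| 20 d | 0.38 | 0.50 / 0.40 / 0.38 | 0.91 / 0.86 / 0.86 |
| 40 d | 0.22 | 0.42 / 0.26 / 0.22 | 0.81 / 0.68 / 0.63 |

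**Threshold.** A deficit of 5% at day 14 needs 2^(−14/T) = 0.05, so T = 14 / log2(20) = 3.2 days. For 10% and 20% deficits, T is 4.2 and 6.0 days. Hence the cut at about 3 days.

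**Effect on the test.** This is the simulated rejection rate of the two-sided 5% signed rank test with no true pregnancy effect, a 12-week gap and 1,000 runs per cell. A given share of women is sampled at day 14 and the rest after 24 weeks on drug. The within-woman CV is assumed.

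| Pairs, CV | Half-life | 25% at day 14 | 50% | 100% |
|---|---|---|---|---|
| 25, 30% | 7 d | 10% | 32% | 91% |
| 25, 30% | 30 d | 49% | 95% | 100% |
| 25, 50% | 7 d | 7% | 17% | 51% |
| 25, 50% | 30 d | 35% | 86% | 100% |
| 12, 30% | 7 d | 7% | 15% | 56% |
| 12, 30% | 30 d | 22% | 66% | 100% |

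At a 1-day half-life the rate stays near 5%. So the problem depends both on the half-life and on how many women are sampled early.

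**The case against.** The case against has several parts.

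- **No affected drug can be shown.** The available text gives no second line drug list, half-life or loading regimen. If every drug in the arm has an effective half-life below about 3 days, nothing follows. This stands, and makes the point conditional.
- **Two weeks is a floor.** The SAP expects some women to finish their TB course before the postpartum visit, so some will have been treated for a long time by the antepartum visit. This also stands. A reader might infer that the antepartum sample is low for every slow drug, or that a false pregnancy effect will be reported. The documents support neither, because they give no distribution of time on drug.
- **The rule may exist elsewhere.** The protocol's eligibility criteria, the separate Pharmacokinetic SAP and the AIP were not available for this check, and a pharmacologist can already declare data unevaluable for a given analysis. So the claim is only that this SAP does not state such a rule. Section 4 assigns the PK comparisons to this SAP, so the rule or a reference to it belongs here.
- **The model is simple.** It has one compartment and no loading. Using a terminal rather than an effective half-life could greatly overstate the deficit, and front-loaded early dosing would weaken or remove it.
- **The stakes are modest.** The second line objective is descriptive, the ratio informs the team's judgement, and time on drug is reported. But it is reported as a demographic summary, which does not link it to individual ratios.

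**Conclusion.** The concern holds in a conditional form. For a second line drug with an effective half-life above about 3 days and no loading, women sampled early can show low antepartum exposure for reasons unrelated to pregnancy, and Stage 2 as written cannot separate the two.

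Under the stated assumptions the bias ranges from negligible (a half-life of 3 days or less, or long prior treatment) to very large (an apparent ratio of 0.42 to 0.22 at day 14 with a 40-day half-life). It shrinks as time on drug grows. Whether it arises in this trial depends on the drug list, any loading and each woman's time on drug, none of which the available text gives.

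A reader might also conclude that the main analysis should be confined to women at steady state. That does not follow. Five half-lives is 100 days at a 20-day half-life and 200 days at 40 days, so the restriction could leave almost no pairs for the very drugs at issue, in an arm already expected to fall short of 25 per drug.

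**What to change.** Keep all pairs as the main Stage 2 analysis. Add to the second line TB paragraph of SAP Section 4:

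> For any second line drug with an effective half-life above about 3 days, the antepartum/postpartum geometric mean ratio is also calculated in women on the drug for at least five effective half-lives at the antepartum visit, and individual ratios are shown against time on drug. If the two estimates differ materially, or too few pairs qualify, the all-pairs ratio is not interpreted as a pregnancy effect, and incomplete accumulation is named as a limitation.

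The SAP should also say where each effective half-life comes from and fix in advance what counts as a material difference and as too few pairs. If the Pharmacokinetic SAP already has a steady-state rule, a reference to it may be enough.

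The cost is SAP wording and a small extra analysis on duration data that the report already summarises. For the slowest drugs the subset will hold few pairs and may only support the limitation statement. Nothing changes in eligibility, sampling or treatment.

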### 2.3.2.6 (For arms in the ARVs without TB Treatment, ARVs with First Line TB Treatment, or Second Line TB Treatment for Drug-Resistant TB with or without ARVs study arm groups).

Objective:

To describe the neonatal elimination of selected ARV and TB drugs acquired across the placenta after maternal dosing during pregnancy.

Outcome measure: Infant washout half-life and concentration of drug after birth (if infants meet the criteria specified in Protocol Section 4.4 for washout PK sampling)

2.3.2.7 To describe pharmacokinetics of ARV drug combinations in HIV-infected women on second line TB treatment\*.

\* Note: These 5 secondary objectives were intended to be exploratory, and will be considered as “Other study objectives”. Therefore, this SAP will not include the outcome measures/analysis contents related to these objectives.

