## **2.4 Overview of Sample Size Considerations**

The sample size calculations will be based on assessing whether therapeutic dosing regimens for the study drugs produce adequate drug exposure during pregnancy as compared to historical data from non-pregnant adults.

Each study arm will enroll a minimum of 12 women and have a target enrollment of 25 women with evaluable 3rd trimester PK data for ARV and TB arms, or evaluable postpartum PK data for oral contraceptive arms. Women who do not have evaluable data will be replaced. Enrollment may be restricted or adjusted so that evaluable 2nd trimester PK data are obtained from at least 12 women. The sample size for an arm may also be increased if additional mothers and infants need to be enrolled to obtain evaluable infant washout PK data. Thus, the total number of participants enrolled per arm may be larger than 25 if women need to be replaced due to non-evaluable data, if additional women need to be enrolled to obtain 2nd trimester PK data, if additional mothers and infants need to be enrolled to obtain infant washout PK data and/or if additional women need to be enrolled to obtain enough second line TB drug data. When combined enrollment in the increased dose darunavir arms reaches 25 participants, the PK data will be evaluated to determine if the data for these arms can be combined and whether enrollment of additional participants in these arms should continue. The actual sample size will be based on the determination of PK exposure parameters, and whether or not the current dose provides adequate drug exposure to pregnant women.

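### SAP section 4 lets an arm's whole infant washout summary be omitted when most values are BLQ, although BLQ at a known time after birth is itself a result for the concentration part of the outcome

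*SAP*

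**What the plan says.** Secondary objective 2.3.2.6 is "To describe the neonatal elimination of selected ARV and TB drugs acquired across the placenta after maternal dosing during pregnancy". Its outcome has two parts: "Infant washout half-life and concentration of drug after birth". It carries no asterisk, so it is not one of the five secondary objectives that the SAP treats as exploratory and leaves out.

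For PK secondary objectives, SAP section 4 plans that "descriptive statistics (mean, median, standard deviation, interquartile range, and range) will be tabulated for PK outcome measures". The exception follows directly: "If most infant washout PK data are below the BLQ for a given study arm", then "the pharmacologist may determine that the analysis report should not include an infant washout PK data summary", with the remark that "this will be noted in the report".

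Three other places bear on this:

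- Section 4 also has a general BLQ rule. Single BLQ values are replaced by half the LLOQ. A profile that is BLQ throughout is reported separately and kept out of the summary analysis.
- Section 5, item 6 (Infant PK analysis) lists "Washout concentration and half-life summary" and states no exception.
- Section 2.4 treats these data as worth extra enrolment: "The sample size for an arm may also be increased if additional mothers and infants need to be enrolled". Section 2.1 says much the same.

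**The concern.** The trigger for omission is the observed result, and the decision is taken once the assay values are known. Values become BLQ when little drug crossed the placenta or when it was cleared before the samples were drawn. Both are findings about the question that the objective asks.

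The rule also treats the two parts of the outcome alike. With few quantifiable points a half-life may not be estimable, and leaving it out loses nothing. Concentration is different, because a value known to lie below a stated limit at a stated time describes the infant's exposure. Under the rule both parts can go, after infants have been sampled and an arm possibly enlarged to obtain the data.

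A reader who sets the separate arm reports side by side could then see washout figures mainly for drugs that persist in the infant, and only a note for the others.

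**Working it through.** The SAP gives no figure for the washout rule, so there is nothing of its own to reproduce. The check is mainly of the text, with illustrations for size.

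**1. How many arms the rule can reach.** Objective 2.3.2.6 names three arm groups. With the counts in section 2.1 these are 10 (ARVs without TB treatment) + 2 (ARVs with first line TB treatment) + 1 (second line TB treatment) = 13 arms. The total is 10 + 2 + 1 + 1 + 4 = 18. So at most 13 of 18 arms are exposed, and only where infants qualified for washout sampling.

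**2. The texts side by side.**

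| Place in SAP | Treatment of a mostly BLQ arm |
|---|---|
| 2.3.2.6 | Half-life and concentration are both outcomes |
| 4, general BLQ rule | Single values at half the LLOQ; all-BLQ profiles reported separately |
| 4, PK secondary objectives | Whole summary may be omitted; a note is made |
| 5, item 6 | Concentration and half-life summary listed, no exception |

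The SAP does not say whether the general BLQ rule covers infants or how it combines with the omission rule. None of these texts requires the number sampled, the number BLQ or the LLOQ when the summary is dropped.

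**3. A mostly BLQ arm can still be summarised (assumed counts).** The number of washout infants per arm is not given. I borrow 12 and 25, the minimum and target numbers of women. Suppose each infant contributes one value, so that infant and arm counts coincide. The exact (Clopper-Pearson) 90% limits for x of n are the 5% point of Beta(x, n−x+1) and the 95% point of Beta(x+1, n−x).

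| BLQ | % | Exact 90% CI |
|---|---|---|
| 13/25 | 52 | 0.341 to 0.695 |
| 20/25 | 80 | 0.625 to 0.918 |
| 25/25 | 100 | 0.887 to 1 |
| 10/12 | 83 | 0.562 to 0.970 |
| 12/12 | 100 | 0.779 to 1 |

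For 25/25 the lower limit is 0.05^(1/25) = 0.887. In every row more than half of the values are BLQ, so the median is known to be below the LLOQ. As a check of method, the same formula at 80% gives (0.131, 0.383) for 6/25, which agrees with the (0.13, 0.38) in section 2.5.

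**4. How the trigger depends on the BLQ proportion.** Read *most* as more than half. For n = 25 the chance of meeting the trigger is P(X ≥ 13), and for n = 12 it is P(X ≥ 7), with X binomial.

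| True BLQ proportion | n = 25 | n = 12 |
|---|---|---|
| 30% | 0.017 | 0.039 |
| 50% | 0.500 | 0.387 |
| 60% | 0.846 | 0.665 |
| 70% | 0.983 | 0.882 |

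**5. How the trigger depends on elimination and transfer.** This is a simulation with assumptions that are not in the documents: 25 infants, first-order decay, samples at 6, 24, 54 and 168 h, log-SD 0.6 for initial concentration and 0.4 for half-life, 4,000 replicates, and *most* meaning more than half of all samples. Entries are the probability that the trigger is met.

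| Initial level | 3 h | 6 h | 12 h | 24 h | 48 h half-life |
|---|---|---|---|---|---|
| 2 × LLOQ | 1.00 | 1.00 | 1.00 | 1.00 | 0.47 |
| 10 × LLOQ | 1.00 | 1.00 | 0.21 | 0.00 | 0.00 |
| 50 × LLOQ | 1.00 | 0.70 | 0.00 | 0.00 | 0.00 |

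A hand check for the middle row: the time to reach the LLOQ is half-life × log2(10) = half-life × 3.32. At 6 h this is 19.9 h, so three of the four samples are BLQ. At 24 h it is 79.7 h, so one of four is. The trigger follows fast elimination and low initial level, as expected. The particular probabilities belong to the assumptions.

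**The case against.** The strongest reply is that the omission is open and sensible. It is disclosed. It is permitted, not required. It concerns a descriptive secondary objective with no test or error rate. A mean, SD or half-life built mostly from values set to half the LLOQ would tell the reader little. Low transfer can still show in the cord-to-maternal ratio (2.3.2.1), which the rule does not touch. All-BLQ profiles would be reported separately if the general rule covers infants. Many BLQ values may also reflect the time since the last maternal dose, the sampling times or the assay's sensitivity. Further BLQ rules may stand in the separate Pharmacokinetic SAP, the AIP or the Protocol, none of which was available for this check.

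Much of this stands, and it limits the point. It does not meet the core of it. The cord-to-maternal ratio is taken at delivery and does not describe elimination. Reporting the LLOQ and sampling times is what would let a reader weigh assay sensitivity and timing. The case for dropping half-life and the mean does not extend to the count of BLQ values.

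Two stronger readings are tempting. A reader might infer that the note will say only that the summary is absent. The SAP leaves the note's content open, and it could state that most values were BLQ. A reader might also infer that a high BLQ proportion at one sampling time triggers omission. The trigger is set on the arm's washout data as a whole, so a late time with many BLQ values does not by itself meet it.

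**Conclusion.** The point holds as a reporting defect that should be corrected. The SAP contains an omission rule that depends on the outcome, has an undefined trigger, and covers a part of the outcome for which BLQ is informative. In an arm with fast elimination or low transfer, objective 2.3.2.6 may be left without figures.

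Its size is modest. At most 13 of 18 arms are exposed, no inference is affected, and the number of arms that would meet the trigger cannot be derived because the SAP gives no BLQ rates. The probabilities in the working show direction only.

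A reader might go further and infer that the trial's washout estimates are biased across arms. The documents do not support that. Section 3 gives each arm its own final report unless the team combines arms, and no cross-arm washout estimate is planned. The selective picture arises only for someone comparing the separate arm reports. Nor does it follow that mostly BLQ arms will go unreported, since the pharmacologist may still choose to summarise them.

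The verdict rests on the SAP text alone. If the AIP or the Pharmacokinetic SAP already requires BLQ counts and LLOQs, the remaining step is to say so in section 4.

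**What to change.** Replace the omission sentence in SAP section 4 with a rule along these lines:

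- Every arm with washout sampling reports, at each sampling time, the number of infants sampled, the number and percentage BLQ, the LLOQ, and the median and range with BLQ values shown as <LLOQ. An exact CI for the percentage BLQ is optional.
- Half-life is given only for infants in whom it can be estimated, with that number over the number sampled.
- Only the half-life summary and the mean/SD may be left out when too few values are quantifiable. The SAP states the threshold and its unit (samples, infants or time points), and the report gives the reason.

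Then state whether the half-LLOQ and all-BLQ-profile rules apply to infants. If they do, say how they fit with the <LLOQ display, and keep infants with all-BLQ profiles in the sampled and BLQ counts. Bring section 5, item 6 into line.

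The cost is one rewritten sentence, a short clarification and one small table per arm from values already assayed. No further sampling is needed.
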